	In Part 2, approximately 246 participants will be randomized 1:1 to 1 of 2 treatment groups (123 participants per group).
Study Design	Part 1 and Part 1 expansion: randomized, open-label Part 2: randomized, double-blind, placebo-controlled
Estimated Duration of Study Participation	 It is estimated that an individual participant may participate for as long as 38 months, which includes the following: up to 28 days for screening. continuous treatment until treatment withdrawal criteria are met or for a maximum of 36 months. a minimum of 30 days for safety follow-up. post-treatment cGVHD follow-up for participants who completed itacitinib/placebo taper after initial response (CR or PR) or discontinued early for reasons other than cGVHD progression and with no requirement for new systemic cGVHD therapy (for a maximum of 24 months from Day 1). participants will be followed for survival until the participant dies or withdraws consent.

Treatment Groups and Duration:

Part 1 is a run-in that will employ a randomized, open-label, parallel-cohort design to assess the safety and tolerability of itacitinib in combination with corticosteroids (Figure 1). A total of 20 participants with moderate or severe cGVHD will be randomized 1:1 to itacitinib 200 mg QD plus corticosteroids or 300 mg QD plus corticosteroids.

[figure not shown]
Part 1 expansion is a Phase 2 with an initial safety run-in that will employ a randomized, open-label, parallel-cohort design to assess the safety and preliminary efficacy of itacitinib in combination with corticosteroids compared with corticosteroids monotherapy and select the appropriate dosing/schedule of itacitinib for Part 2 (Figure 2). A total of 140 participants (including those from Part 1) with moderate or severe cGVHD will be randomized 1:1 to 1 of 4 treatment groups that are itacitinib 300 mg QD plus corticosteroids (Treatment Group A), itacitinib 400 mg QD plus corticosteroids (Treatment Group B), itacitinib 300 mg BID plus corticosteroids (Treatment Group C) or corticosteroids monotherapy (Treatment Group D). Treatment Group C was discontinued as of Amendment 8. Randomization will be stratified by

cGVHD risk status (moderate vs severe). Treatment Groups B and C will have an initial safety run-in of 10 participants each to determine safety and tolerability of the dose before expanding.

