Itacitinib treatment will continue until treatment failure (cGVHD progression, death, or initiation of new systemic cGVHD therapy), unacceptable toxicity, or withdrawal of consent and for a maximum of 36 months.

[figure not shown]
Part 2 will employ a randomized, double-blind, placebo-controlled design in order to assess the efficacy of itacitinib in combination with corticosteroids using the dose determined to be safe and tolerable in the Part 1 expansion (Figure 1 and Figure 2). Randomization will be stratified by cGVHD risk status (moderate vs severe). Participants randomized to the placebo group will be permitted to cross over to the experimental group after completion of the primary analysis as appropriate. All participants will be followed for survival after completion of study treatment.

Figure 1: Study Design Schema

Note: Treatment Group C discontinued as of SEP 2021.

Figure 2: Treatment Phase, Post-Treatment, and Survival Follow-Up

Adherence to the study design requirements, including those specified in the schedule of activities (Table 4), is essential and required for study conduct.

Table 4: Schedule of Activities

											Follow-Up)	
	Screening					Treatn	nent			Safety	GVHD ^a	Survival	
Visit Day (Range)	Day -28 to -1	D1	1	D14		D28/56/84/ 112/140/168			ЕОТ	Last Dose + 30 days	Q28D/ Q8W°	Q8W From EOT	Notes
Visit Window			±	3 da	ys		±	7 days		+ 5 days	± 7 days	± 14 days	
Administrative procedures	1				ı	1		T		1	r	T	T
Informed consent	X												
Inclusion/exclusion criteria	X												
Demography	X												
Relevant medical history	X												
Prior/concomitant medications	X					X			X	X			
Randomize using IVRS	X												
Contact IVRS/dispense study drug		X				X		X	X				
Administer study drug						X							Hold treatment on clinic visit days until blood draws complete
Administer corticosteroids						X							
Distribute reminder cards						X							
Monitor study drug compliance						X			X				
Monitor corticosteroid use						X			X				
Safety assessments													
AE assessments	X					X			X	X			
Physical exam/vitals/weight	X					X			X	X	X*		*Only weight
KPS	X					X			X	X			
Infection monitoring	X		X*						X*	X*			*As clinically indicated
Graft failure/chimerism*	X ^d					Х*			X*	X*	X*		*As clinically indicated
12-lead ECG	X								X				
Efficacy assessments	Т	1		1		1		T		Т	ı	Γ	T
cGVHD diagnosis and staging	Xe												
cGVHD response		Xf		X		X	X	X	X	Xa	Xa		

Table 4: Schedule of Activities (Continued)

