^c Every 28 days (± 7 days) up to 1 year (D364) from Day 1 and then every 8 weeks (± 7 days) up to 2 years from Day 1.

d Chimerism testing can be performed on Day 1 before study drug administration. Results are not required for randomization and treatment.

^e Chronic GVHD staging (see criteria in Appendix C) performed at screening will be used for eligibility assessment and stratification purposes

f Chronic GVHD organ score and overall severity score 0 to 10 (see criteria in Appendix E) will be performed on Day 1, and this will be the baseline for cGVHD response assessment during treatment and post-treatment follow-up.

g FEV1% performed within 7 days of Day 1 can be used for cGVHD response assessment if bronchiolitis obliterans was not diagnosed at screening.

h May be performed within 7 days of Day 1. If liver cGVHD is diagnosed at screening, total bilirubin, ALT, and ALP should be repeated on Day 1.

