6.2. Measures to Minimize Bias: Randomization and Blinding

All participants will be centrally assigned to study treatment using an IVRS. Before the study is initiated, the telephone number and call-in directions for the IVRS and/or the login information and directions for the IVRS will be provided to each site. Full details will be provided in the IVRS section of the Study Manual.

Study treatment will be dispensed at the study visits summarized in the schedule of activities (Table 4).

Returned study treatment should not be redispensed to the participants.

Centralized randomization numbers within each stratum will be created for treatment assignment. Participants will be assigned to study drug cohorts in accordance with the randomization schedule. In Part 1, the participant, the investigator, and the sponsor will be aware of each treatment assignment; in Part 2, they will remain blinded to treatment assignment.

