8.1.2. Screening Procedures

Screening is the interval between signing the ICF and the day the participant is randomized in the study (Day 1). Screening may not exceed 28 days. Assessments that are required to demonstrate eligibility may be performed over the course of 1 or more days during the screening process.

Procedures conducted as part of the participant's routine clinical management (eg, blood count, hepatitis serology) obtained before signing of informed consent may be used for screening or baseline purposes provided the procedure meets the Protocol-defined criteria and has been performed in the timeframe of the study. For participants who are randomized in the study, information associated with eligibility requirements must be entered into the appropriate eCRF.

Results from screening visit evaluations will be reviewed by the investigator to confirm eligibility before randomization or the administration of study treatment. Tests with results that do not meet eligibility requirements may be repeated once during screening if the investigator believes the result to be in error or believes there has been a change in eligibility status (eg, following recovery from an infection). For screening assessments that are repeated, the most recent available result before randomization will be used to determine eligibility. Treatment should start as soon as possible, but within 2 days after the date of randomization.

Screening and randomization may occur on the same day provided all assessments have been completed and eligibility has been confirmed.

See Sections 5.4 and 5.5 for information regarding screen failures and replacement of participants, respectively.

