8.2.2. Chronic GVHD Response Assessment

Chronic GVHD organ scoring and the overall severity score 0 to 10 will be assessed on Day 1 (ie, baseline). Postbaseline response evaluations will be performed by the treating physician according to the detailed schedule in Table 4. At each postbaseline assessment, each organ must be assessed using the same criteria as for baseline, and response should be determined by comparing the current organ assessment with the baseline organ assessment on Day 1. A high level summary of organ-specific response assessment criteria as per NIH consensus guideline (Lee et al 2015, Appendix E) are listed in Table 18 and Table 19.

Table 18: Organ Assessments

Organ	Evaluation	Criteria
Skin	NIH Skin Score, considering %BSA involvement and sclerotic features	Change of Skin score
Eyes	NIH Eye score	Change of Eye score
Mouth	NIH Modified OMRS (sum of scores for erythema, lichenoid, and ulcers)	Change of OMRS
Esophagus	NIH Esophagus score	Change in Esophagus score
Upper GI	NIH Upper GI score	Change in Upper GI score
Lower GI	NIH Lower GI score	Change of Lower GI score
Liver	Lab results for ALT, ALP, and total bilirubin	Change in values of lab results
Lungs	NIH Lung score and FEV1% (in participants using a bronchodilator, the post-bronchodilator response should be used for response assessment)	Change in FEV1%
Joints and fascia	NIH Joint and Fascia score and P-ROM scores	Change of Joint and Fascia score and P-ROM scores

Table 19: Postbaseline Response Evaluations

Organ	Organ Specific Response				
Skin	CR/not involved	PR in at least	PR or CR in 1 or	Progression in	Organ-specific
Eyes		1 organ with baseline	more organ(s) with baseline	1 or more	response 'unchanged' for
Mouth		involvement	involvement	organ(s) with baseline	all organs (incl.
Esophagus		AND .	AND	involvement	no involvement)
Upper GI		no progression in any other	progression in 1 or more	OR new occurrence	
Lower GI		organ (ie, CR,	organs (incl.	in an organ with	
Liver		PR, unchanged,	new occurrence	no baseline	
Lungs		or no involvement)	in an organ with no baseline	involvement AND	
Joints and fascia			involvement)	no CR or PR in any other organ	
Overall Response	CR	PR	MR	PD	Unchanged

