APPENDIX E. RESPONSE ASSESSMENT FOR CHRONIC GVHD (NIH CRITERIA)

Response will be assessed using NIH 2014 criteria (Lee et al 2015)

a) Response determination for cGVHD by organ at postbaseline assessment

(comparison versus baseline)

Organ	Complete Response	Partial Response	Progression
Skin	NIH Skin Score 0 after previous involvement	Decrease in NIH Skin Score by 1 or more points	Increase in NIH Skin Score by 1 or more points, except 0 to 1
Eyes	NIH Eye Score 0 after previous involvement	Decrease in NIH Eye Score by 1 or more points	Increase in NIH Eye Score by 1 or more points, except 0 to 1
Mouth	NIH Modified OMRS 0 after previous involvement	Decrease in NIH Modified OMRS of 2 or more points	Increase in NIH Modified OMRS of 2 or more points
Esophagus	NIH Esophagus Score 0 after previous involvement	Decrease in NIH Esophagus Score by 1 or more points	Increase in NIH Esophagus Score by 1 or more points, except 0 to 1
Upper GI	NIH Upper GI Score 0 after previous involvement	Decrease in NIH Upper GI Score by 1 or more points	Increase in NIH Upper GI Score by 1 or more points, except 0 to 1
Lower GI	NIH Lower GI Score 0 after previous involvement	Decrease in NIH Lower GI Score by 1 or more points	Increase in NIH Lower GI Score by 1 or more points, except from 0 to 1
Liver	Normal ALT, alkaline phosphatase, and Total bilirubin after previous elevation of 1 or more	Decrease by 50%	Increase by 2 × ULN
Lungs	Normal FEV1% after previous involvement If PFTs not available, NIH Lung Symptom Score 0 after previous involvement	Increase by 10% predicted absolute value of FEV1% If PFTs not available, decrease in NIH Lung Symptom Score by 1 or more points	 Decrease by 10% predicted absolute value of FEV1% If PFTs not available, increase in NIH Lung Symptom Score by 1 or more points, except 0 to 1
Joints and fascia	Both NIH Joint and Fascia Score 0 and P-ROM score 25 after previous involvement by at least 1 measure	Decrease in NIH Joint and Fascia Score by 1 or more points or increase in P-ROM score by 1 point for any site	Increase in NIH Joint and Fascia Score by 1 or more points or decrease in P-ROM score by 1 point for any site
Global	Clinician overall severity score 0	Clinician overall severity score decreases by 2 or more points on a 0-10 scale	Clinician overall severity score increases by 2 or more points on a 0-10 scale

Source: Adapted from Lee et al 2015.

b) Response assessment for chronic GVHD by organ at baseline and at each post-baseline visit

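### In the open-label Part 1 expansion nothing requires the cGVHD response baseline to be scored before the treatment assignment is known, so the comparison with corticosteroids alone can be tilted through the baseline

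*Protocol*

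**What the plan says.** Protocol Table 3 describes the design as "Part 1 and Part 1 expansion: randomized, open-label". Section 6.2 adds: "In Part 1, the participant, the investigator, and the sponsor will be aware of each treatment assignment".

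In Table 4 the row "Randomize using IVRS" is marked in the screening column (Day -28 to -1). The cGVHD response row starts in the Day 1 column, and footnote f says the organ and 0-10 severity scores "will be performed on Day 1, and this will be the baseline for cGVHD response assessment during treatment and post-treatment follow-up". Section 8.2.2 repeats this for every later visit: "response should be determined by comparing the current organ assessment with the baseline organ assessment on Day 1". Footnote e limits the screening staging to eligibility and stratification.

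On timing, Section 8.1.2 says: "Treatment should start as soon as possible, but within 2 days after the date of randomization". The same section also defines screening in a way that equates randomization day with Day 1: "Screening is the interval between signing the ICF and the day the participant is randomized in the study (Day 1". SAP 4.1.1 instead ties Day 1 to the first dose. SAP 4.1.3 requires a baseline value to precede first dose and is silent on whether it precedes assignment. SAP 6.1.2 takes baseline organ involvement from Day 1.

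Under Appendix E, partial response in most clinician-scored organs needs a 1-point fall; for skin the rule is "Decrease in NIH Skin Score by 1 or more points".

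**The concern.** The IVRS keeps the assignment hidden until a participant is enrolled, but it does not protect a baseline recorded after the call. Response is a change score, so a clinician who knows the arm can influence it at both ends. Neither document asks for the baseline scores to be entered before assignment, for a blinded scorer, or for central review.

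A single baseline score carries into Months 3, 6 and 12. Month 3 and Month 6 response rates are the key secondary endpoints of the expansion. They are summarized to support the Part 2 dose, the Month 6 rate feeds the Table 23 posterior, and it is tested in exploratory CMH comparisons of Groups A and B with Group D. If itacitinib baselines run high, or Group D baselines run low, the contrast with corticosteroids alone looks better than it is.

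**Working it through.** **1. Order of events.**
- Table 4: randomization in screening, response baseline on Day 1.
- SAP 4.1.1 and Section 8.1.2: Day 1 is first dose, 0 to 2 days after randomization.
- Section 8.1.2, definition of screening: Day 1 is the randomization day.

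Under the first two, the baseline falls on or after the day of assignment. Under the third, scoring could come before or after the IVRS call on the same day. No passage rules out scoring after the call.

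**2. Which organs are exposed.** Liver response uses ALT, ALP and bilirubin, and lung response uses FEV1% where available; these are objective. Skin, eyes, mouth, GI, and joints and fascia are scored by a clinician. Table 19 gives an overall PR for a PR in one involved organ with no progression elsewhere. A participant whose true eye score is 1 at baseline and 1 at Month 6 is unchanged; recorded as 2 at baseline, the same participant is a PR. The mouth scale needs 2 points.

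**3. Table 23 reproduced.** Take independent posteriors p ~ Beta(a + s, b + 35 - s) in each group and compute P(p_itacitinib - p_control > d). The prior and margin d are not visible in the text, so both are assumptions. With a = b = 1 and d = 0.15, all 30 cells are reproduced to within 0.05 percentage points, including 45.0% for 25 versus 20 responders.

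**4. What one reclassified participant does.** From Table 23, with 20/35 responders in Group D:

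| Itacitinib responders | Posterior | Step |
|---|---|---|
| 25 | 45.0% | |
| 26 | 54.9% | +9.9 |
| 27 | 64.7% | +9.8 |
| 28 | 73.9% | +9.2 |

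Each step is 1/35 = 2.9 points of response rate. One participant gained by itacitinib and one lost by Group D (26 versus 19) gives 64.4%.

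**5. Plausible size of the shift.** The documents give no rate of over-scoring, so this is illustrative:

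shift = P(over-scored) x P(nonresponder) x P(unchanged, given nonresponder)

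- P(over-scored): 0.10 to 0.30, assumed.
- P(nonresponder): 10/35. Table 23's itacitinib rows start at 25/35 responders, so 10 is the most nonresponders it contemplates.
- P(unchanged): 0.5 to 1.0, assumed.

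Low end: 0.10 x 10/35 x 0.5 = 1.4 points (0.5 of 35 participants). High end: 0.30 x 10/35 x 1.0 = 8.6 points (3 of 35).

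SAP 7.3.1 also counts death, new systemic therapy, withdrawal, hematologic progression and a missing assessment as nonresponse. A higher baseline score cannot convert these, which pulls the shift down. A higher baseline can also hide true progression (a change from 1 to 2 recorded as 2 to 2), a route that the formula leaves out.

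**6. How many participants a reordering can still reach.** Section 2.3.2.3 reports 32, 25 and 26 enrolled in A, B and D by 09 JUL 2021, a total of 83. The plan is 3 x 35 = 105, which leaves at most 105 - 83 = 22.

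**The case against.** The strongest reply is that the plan does not say the baseline is scored after assignment. Section 8.1.2 equates randomization day with Day 1 and lets screening and randomization share a day, so scoring may come first. Nor is the Day 1 scorer named: Section 8.2.2 names the treating physician only for postbaseline visits. Both points stand. A reader might infer that every baseline is scored by an investigator who knows the arm. The documents permit that, and Table 4's layout implies the order, but they do not establish it.

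A reader might also infer that the Part 2 dose choice is compromised. SAP 7.2 makes dose selection primarily a matter of adverse events, with response in support, and the protocol says only that the posterior may be used. With Group C closed, the choice is between two open-label itacitinib arms, and a tilt in itacitinib's favour would affect both alike and largely cancel. The exposed quantities are the Table 23 posterior and the exploratory CMH contrasts with D. No formal efficacy test is planned in the expansion, and Part 2 is double-blind.

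Month 3 and Month 6 scoring is itself unblinded, so protecting the baseline closes only one of two routes. That is true. It is the route that can be closed by changing the order of two existing steps, without extra readers.

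**Conclusion.** The point holds as a gap in the protection against bias. As written, the plan allows an arm-aware baseline for every response in the Part 1 expansion, and no planned analysis would detect it. The bias would bear on itacitinib against corticosteroids alone, and much less on A against B.

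Each reclassified itacitinib participant moves the posterior by about 9 to 10 points in the part of Table 23 examined. Under the stated assumptions the response rate shifts by about 1.4 to 8.6 points. Those bounds rest on an assumed 10-30% over-scoring rate, on over-scoring being unrelated to later response, and on half to all nonresponders being merely unchanged.

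Two stronger readings are not supported. Applying 15/35 nonresponders would raise the upper end to 0.30 x 15/35 = 12.9 points, but that is Group D's nonresponse in the example; no itacitinib row in Table 23 has more than 10/35. Nor is the bias beyond detection: Section 8.2.1 requires all organs to be staged at screening, so a differential shift by Day 1 can be examined with data already collected.

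**What to change.** 1. **Protocol, Table 4 footnote f and Section 8.2.2.** For participants still to be randomized in the Part 1 expansion, require the baseline organ scores and the 0-10 severity score to be completed and entered before the IVRS is contacted for treatment assignment. Reconcile the Day 1 definition in Section 8.1.2 with Table 4 and SAP 4.1.1.
2. **SAP 7.3.1.** Compare the screening-to-Day 1 change in organ scores across Groups A, B and D for organs on the same 0-3 scale at both times (skin, eyes, joints and fascia). Randomization should balance genuine change over that interval, so a difference between arms would be informative. Add a supportive organ-level analysis of Month 3 and Month 6 response with the screening scores as baseline.

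Because the reordering can reach at most about 22 participants, the SAP comparison carries most of the value.

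No new visit, procedure or sample size is needed. The costs are a protocol amendment with IRB/IEC approval, a baseline that may be up to 2 days older than first dose, and a small amount of added SAP output. The check has limits: screening scores may be up to 28 days old, they do not cover the mouth and GI response scales, and postbaseline scoring stays unblinded.

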2. INTRODUCTION

2.1. Chronic GVHD Background

Allogeneic hematopoietic stem cell transplantation is an effective immunotherapy for patients with blood-related malignancies and hematologic disorders. More than 32,000 allo-HCTs are performed each year worldwide, primarily for the treatment of hematologic malignancies (Niederwieser et al 2016). Acute GVHD (aGVHD) and cGVHD remain major contributors to transplantation-related deaths and are the most significant barrier to successful allo-HCT. GVHD pathogenesis is driven by a number of risk factors, including donor/recipient HLA mismatch, increased age (donor or recipient), sex, intensity of the pretransplant conditioning regimen, and donor source (Jagasia et al 2012, Flowers et al 2011). In short, donor-derived immune cells recognize the transplant recipient as foreign, which leads to an inflammatory cascade and proliferation of immune effector cells. Left uncontrolled, these processes can lead to extensive tissue damage and potential organ failure in the transplant recipient (Holtan et al 2014).

The prevalence and severity of cGVHD, occurring in 30% to 70% of allo-HCT patients (Lee and Flowers 2008) has increased over the past 2 decades due to several factors, including the increased use of mobilized peripheral blood stem cell grafts (containing higher numbers of donor T-cells than BM), advanced age of transplant recipients rising from 55 to 75 years due to development of better tolerated reduced intensity conditioning, and improvements in survival during the first months after allo-HCT. Chronic GVHD is classified into mild, moderate, and severe categories based on the degree of organ involvement according to NIH Consensus Criteria; approximately 50% of patients diagnosed with cGVHD have disease present in 3 or more organ systems (Jagasia et al 2015). Standard initial treatment of moderate and severe cGVHD includes systemic corticosteroids at a prednisone dose ranging between 0.5 to 1 mg/kg per day and may also include cyclosporine, tacrolimus, or sirolimus. Prolonged exposure to high doses of corticosteroids has been associated with a number of significant AEs, requiring clinicians to initiate a corticosteroid taper once responses are observed. Approximately half of cGVHD patients are able to discontinue corticosteroids within the first 7 years of treatment; 10% require prolonged treatment beyond 7 years, and the remaining 40% develop MR or die due to non-relapse-related causes within the first 7 years (Martin et al 2015).

